PARTICIPATING STUDY SITE - Oregon Health & Science University (OHSU)

PRÉCIS

Study Title: Local Effects of Acupuncture on the Median and Ulnar Nerves in Patients with Carpal Tunnel Syndrome (CTS): A Pilot Mechanistic Study

Objectives: The purpose of this study is to measure the local effects of acupuncture on the median and ulnar nerves in patients with median neuropathy at the wrist (carpal tunnel syndrome), using nerve conduction studies (NCS) and quantitative sensory testing (QST) as outcomes. Our secondary aim is to compare acupuncture's effect on the functioning of a diseased nerve (median nerve in CTS) to its effect on a healthy nerve (ulnar). Additionally, we aim to compare the local, nerve-specific effect of manual acupuncture to that of low-frequency electroacupuncture and of high-frequency electroacupuncture.

Design and Outcomes: In a mechanistic study of acupuncture, 60 subjects with carpal tunnel syndrome (CTS) will be randomized to manual acupuncture (MA), low-frequency electroacupuncture (LF-EA) and high-frequency electroacupuncture (HF-EA) groups. Baseline measurements will consist of QST (vibration and cold detection thresholds), as well as NCS of both median and ulnar nerves. Then, each group will undergo acupuncture to the median nerve (Pericardium channel points) and to the ulnar nerve (Heart channel points), one week apart, order counterbalanced, followed by post-acupuncture NCS and QST measurements in both nerves (**See Figure 1 below**).

During the study initial visit (Week 1) baseline QST and NCS measurements will be obtained, followed by acupuncture (manual, low- or high-frequency) intervention to the ulnar or to the median nerve (based on treatment randomization) and repeat post-intervention QST and NCS measurements to both median and ulnar nerves.

[figure not shown]
During the study second and final week (Week 2), baseline QST and NCS measurements will be obtained again, followed by acupuncture (MA, LF-EA, HF-EA) intervention to the nerve, which was not treated the first week. Finally, repeat post-acupuncture QST and NCS measurements will be obtained in both median and ulnar nerves (**see Figure 1 below**).

Interventions and Duration : Subjects will be randomized to 3 intervention groups as specified above: Manual, Low-frequency and High-frequency electroacupuncture. Each subject will receive the following interventions:

1. Acupuncture to PC3, 5 overlying the median nerve
2. Acupuncture to HT3,4 overlying the ulnar nerve

These will be performed one week apart, in random order. Each acupuncture session will involve 2 needles, with active treatment time 20 min and needle retention during the subsequent QST measurement. Needles will be taken out prior to the post-acupuncture NCS measurements.

Fig.1. Study Procedures Flowchart

Abbreviations: NCS=nerve conduction studies, QST=quantitative sensory testing, CDT=cold detection threshold, VDT=vibration detection testing, MA= manual acupuncture, LF-EA=low-frequency electroacupuncture, HF-EA=high-frequency electroacupuncture, MN = median nerve, UN = ulnar nerve

Sample Size and Population: We plan to enroll 60 subjects with mild-moderate carpal tunnel syndrome, ages 18-75, male and female. In addition to basic eligibility criteria described in detail below and based on a subject’s medical history, we anticipate the need to screen 75-80 subjects in the lab with baseline QST and NCS in order to make the determination for study eligibility (see Figure 1 above). Subjects will be recruited from OHSU’s EMG lab and neuromuscular clinic.

Once determined eligible and meeting the baseline QST and NCS enrollment criteria, subjects will be randomized using stratified randomization (with stratification factors of age and gender), to 3 groups of 20 subjects each - Manual Acupuncture (MA) group, Low-frequency Electroacupuncture (LF-EA) group and High-frequency Electroacupuncture (HF-EA) group.

1. STUDY OBJECTIVES

1.1. Primary Objective

Specific Aim 1: Characterize the effects of acupuncture on QST (cold and vibration sensation thresholds) and nerve conduction study parameters in the Median and Ulnar nerves.

Hypothesis: Acupuncture will cause decrease in cold and vibration detection thresholds (improve sensation) in the underlying nerve sensory distribution only. Acupuncture will cause NCS changes, characteristic of improved nerve function.

1.2. Secondary Objectives

Specific Aim 2: Compare the effects of acupuncture on a diseased nerve (Median) to those of a healthy nerve (Ulnar), using QST (cold and vibration sensation thresholds) and NCS parameters.

Hypothesis: There will be greater change in cold and vibration detection thresholds and NCS parameters in the median nerve compared to the ulnar, due to the lower functional baseline of the median nerve.

Specific Aim 3: Compare the effects of manual acupuncture to those of low-frequency and high-frequency electroacupuncture.

Hypothesis: High-frequency electroacupuncture will have greater effect on NCS, QST followed by low-frequency electroacupuncture and manual acupuncture, in accordance to traditional practices.

2. BACKGROUND AND RATIONALE

2.1. Acupuncture Background

Acupuncture is an ancient therapeutic modality, traditionally involving needling techniques, based on ancient Chinese theories of acupoints located along energy channels called meridians. More recently acupuncture has emerged as an important integrative medical treatment, both in the hospital and outpatient setting (1, 2). In 1998 an NIH Consensus Development Panel concluded that acupuncture is efficacious in adult post-operative and chemotherapy-induced nausea and vomiting, and that acupuncture is helpful in other conditions, including stroke rehabilitation (3). More recent evidence-based reviews have shown the therapeutic benefits of acupuncture for chronic low-back pain (44, 45), migraine and tension headache (46, 47), chemotherapy-induced nausea and vomiting (48), among other conditions.

In spite of acupuncture's increased acceptance, its mechanism of action remains unknown. There is debate as to whether there is point-specific response in acupuncture or whether it induces a more generalized response, perhaps related to endogenous opioid or placebo response. Early research suggested that the effects of acupuncture are mediated on a systemic level by the endogenous opioid system (4, 5, 6). Acupuncture seems to increase cerebrospinal fluid levels of endorphins, enkephalins, and adrenocorticotrophic hormone and its effect can be blocked by the endorphin antagonist naloxone (4, 6). The immune effects of acupuncture seem to be mediated

via increased activity of splenic NK cells and levels of interferon-gamma (7). Acupuncture may also affect the gene expression of neuropeptides and their receptors (8, 9). A centrally acting agent/mechanism, however, cannot explain why acupuncture is conventionally applied in close proximity to the locus of pain and why the analgesic effects of acupuncture are often limited to the ipsilateral side (10, 11).

For many decades acupuncture practitioners and anatomists have attempted to correlate the location of acupuncture points to peripheral nerves, spinal segments and spinal plexuses (12-17, 18). This neuroanatomical theory of acupuncture suggests that acupuncture's effect is mediated via afferent input through the peripheral nervous system, eliciting a reflex at the level of the spinal cord via the sympathetic plexuses and via efferent to the visceral organs and skeletal muscle (19, 20). The neurophysiologic testing to support these theories is lacking so far and further study on the local effects of acupuncture on the peripheral nervous system is needed. There is a consensus, however, that the nervous system is vital in processing the effects of acupuncture.

2.2. Significance

The lack of understanding of acupuncture's mechanism of action is a major obstacle to its wider acceptance. The lack of objective physiologic measurements of acupuncture's effect has posed many difficulties in designing acupuncture research studies involving dose response and efficacy.

Our research will address this knowledge gap by measuring the local effects of acupuncture on an underlying nerve by focusing on Nerve Conduction Study (NCS) parameters and Quantitative Sensory Testing (QST) in the territory of that nerve. Additionally, we will isolate these effects by comparing them to those of a neighboring nerve. Quantifying acupuncture's effects using physiologic parameters and discreet values could standardize treatment regimens and measure therapeutic effect in tangible ways. As acupuncture practices vary widely, with various treatment modalities and point selection, the ability to measure direct effects on the peripheral nerves may help compare treatment regimens and standardize practices by developing efficient protocols.

This line of research is expected to substantiate the proposed association between acupuncture meridians and peripheral nerves in the arm and leg and translate the explanatory constructs of channels and Qi, drawn from TCM into an acceptable western physiologic paradigm of nerve physiologic changes based on redistribution of charge.

2.3. Innovation

While fascia changes have been implicated in chronic pain conditions (50), likely mediated by a local inflammatory response, the analgesic effects of acupuncture cannot be explained by fascia changes alone, without involvement of the nervous system. Langevin and Sherman (51) recently hypothesized that acupuncture causes changes in mechano- and nociceptive receptors in connective tissue. Recent histological studies of fascia have shown it to be very rich in Ruffini and Pacinian corpuscles and free nerve endings and it is therefore believed to be involved in proprioception (32). The proposed research is innovative, in our opinion, because it does not seek to disprove or adopt the fascia mechanistic theory of acupuncture, but rather focuses on the

peripheral nervous system's processing of acupuncture as a final common pathway before further mediation and potentiation occur at the level of the spinal cord and cerebrum.

QST and NCS have both been used in acupuncture research before, however their use has been to assess therapeutic clinical improvements in the patient (21, 42). These measurements have never been targeted to a particular nerve distribution and used to study anatomical correlations between acupoints/channels and an underlying peripheral nerve, with the goal of assessing for acupuncture-induced functional changes in the nerve. We hope that this line of research will lead to a cohesive understanding of acupuncture's mechanism of action, which incorporates the fascia and the peripheral nervous system effects.

2.4. The “DeQi” Sensation and the Peripheral Nerves

According to traditional acupuncture teachings, it is essential to elicit a sensation called “DeQi”, in order to achieve therapeutic results. This sensation is accomplished by manipulation of the acupuncture needle after its insertion in the acupuncture point. It has been described as aching, soreness, heaviness/pressure, fullness, warmth, coolness, tingling, numbness and dull pain at the site of the needle (29) or radiating paresthesias (30). It appears that this sensation is mediated by the peripheral nerves. In clinical practice patients often report that manipulation of the acupuncture needles causes a sensation “like hitting one's funny bone” and neuropathy patients, when undergoing acupuncture of local points in the feet, liken the sensation to an exacerbation of their neuropathy symptoms. Langevin et al (31) have suggested that the sensation of DeQi is elicited by fascia manipulation, however muscle fiber contraction surrounding the needle remains a possibility. From a neurologic perspective, both muscle or fascia manipulation would result in mechanical compression and possibly release of inflammatory factors, leading to small and larger peripheral nerve fiber activation.

2.5. Introduction to Acupuncture Modalities – Manual and Electroacupuncture

Manual acupuncture consists of placing needles in acupuncture points, at a point-specific pre-determined depth, based on established guidelines from the Traditional Chinese Medicine literature. Following insertion the needles are manually manipulated with rapid clockwise or counter-clockwise rotation or small vertical adjustments in the scale of millimeters. This manipulation (aka needle stimulation) is carried out for 45 sec – 1-2 minutes, typically until the subject feels the “De Qi” sensation. The needles are then left in for 15-20 minutes. Often times a second stimulation session is performed midway in the course of the treatment, depending on the acupuncturist's style of practice.

Electroacupuncture is an acupuncture modality, which gained wide acceptance in the 1950s simultaneously in China, Germany and Japan (43). It consists of placing acupuncture needles in traditional acupuncture points, then connecting them to an electrostimulating device. Electrical current is applied to connect 2 needles to an anode and cathode. Typically alternating current in the range of 10-80 milliamps is applied, with a voltage range of range of 40-80 volts. Frequency varies from 2-100 Hz. In general lower frequencies (2-10Hz) are considered to be toning/stimulating of the nerves and higher frequencies (80-100 Hz) are considered inhibitory and are used for analgesia (43). Typical electroacupuncture treatment usually lasts 10-20 minutes.

2.6. Quantitative Sensation Testing (QST)

Computer-assisted Sensory Evaluation (CASE) aka Quantitative Sensation Testing (QST) has been in clinical use since the late 1970s, when Dyck, O'Brien et al introduced the concept of an automated system to evaluate touch-pressure vibration and thermal cutaneous sensation (38). QST is administered in a lab and consists of standardized, precisely delivered computer-generated stimuli, based on careful study of physiologic perception thresholds and “just noticeable difference (JND)” of heat, cold, vibration and touch-pressure (39). Typically the lateral side of the nail bed is used to assess vibration detection threshold (VDT) in the hand and the dorsal surface of the hand is used to assess cooling (CDT) or heating detection threshold.

Fig.2. CASE IV Vibration Stimulator

[figure not shown]

[figure not shown]
Fig.3. CASE IV Thermal Stimulator

The creators of the CASE system created various algorithms for assessing hyper- and hypoalgesia in peripheral neuropathy patients. QST performed with the fourth generation system (CASEIV) have been shown to be efficient, reproducible, and validated against other algorithms of sensory testing (40). The correlation coefficients for vibratory detection threshold (VDT) and cooling detection threshold (CDT) have been found by greater than 0.9 (40). While QST has become a widely-used research tool, the validity of its results is highly dependent on the subject's ability to cooperate and sustain focused attention on stimulus presentation. Therefore, QST cannot be administered when the patient is inattentive, uncooperative, demented, sedated, or too ill to cooperate.

2.7. Study Rationale - Acupuncture for Carpal Tunnel Syndrome, PC6 and the Median Nerve

One area of acupuncture research, which has yielded successful results, is the efficacy of acupuncture in the treatment of Carpal Tunnel Syndrome (CTS). Acupuncture has shown to be effective for mild-moderate CTS with lasting effects on Nerve Conduction Studies (NCS) a year post-treatment (21). Additionally, laser acupuncture and TENS applied to the wrist has been shown to be effective in the treatment of CTS, with symptom improvement still present on 1-3 year follow-up (22, 23). Interestingly the above treatment protocols all involved acupuncture regimens with needles placed in the Pericardium channel (PC), most commonly PC6 (21, 24) and PC7 (21, 22, 23, 25) and PC3 (25), see **Figure 4** below.

Fig.4. Anatomical Correlation of the Pericardium Meridian/Channel and the median nerve

Pericardium Meridian

The anatomical connection of the acupuncture point PC6 and the Median nerve has been well established both in cadavers (26) and in live subjects using ultrasound (27, 28), most strikingly with a documented case of the acupuncture needle piercing through the Median nerve sheath, with absence of any symptoms in the subject (28).

All these studies raise the question of the effect of acupuncture in the Pericardium channel on the underlying Median Nerve.

3. STUDY DESIGN

This is a pilot mechanistic study in which the local effects of acupuncture on the median and ulnar nerves will be investigated, by applying acupuncture to points in the Pericardium and Heart meridians, which appear to track the path of the median and the ulnar nerves, respectively (see **Figure 5 below**). All subjects will have a diagnosis of carpal tunnel syndrome, which is a median nerve entrapment at the wrist.

Subjects will be randomly allocated to one of 3 intervention groups – manual acupuncture (MA), low-frequency electroacupuncture (LF-EA) and high-frequency electroacupuncture (HF-EA). All subjects will have a diagnosis of carpal tunnel syndrome (median nerve entrapment at the wrist). The intervention will be acupuncture (MA, LF-EA or HF-EA) and the outcome variables – post-acupuncture NCS of the median and ulnar nerves and quantitative sensory testing (QST) measurements in the palmar median and ulnar nerve distributions (specifically cold and vibration detection thresholds), see **Figure 1** above. In each group there will be 2 treatments in random order, in which acupuncture will be applied to the median nerve/Pericardium meridian and the ulnar nerve/Heart Meridian.

Fig.5. Anatomic correlation of the median nerve and Pericardium Channel (PC) and of the ulnar nerve and Heart Channel (HT).

The healthy ulnar nerve will serve as a control in two ways:

1. Local Effects - the ulnar nerve, being in close proximity to the median nerve, will be investigated for possible effects when acupuncture is delivered to Pericardium channel points (over the median nerve). In this way we will explore whether acupuncture has effects only on the underlying nerve, or also on a neighboring nerve. This will be accomplished by measuring post-acupuncture QST and NCS in both the median and ulnar nerves, when the intervention is done over the median nerve.

Hypothesis: Acupuncture will cause decrease in cold and vibration detection thresholds (improve sensation) in the underlying nerve sensory distribution only. Acupuncture will cause NCS changes, characteristic of improved nerve function.

2. Healthy vs Diseased nerve Effect – The intervention will be delivered over the ulnar nerve (healthy) as well, using Heart channel acupuncture points. This will enable us to compare the acupuncture effect on a healthy nerve, compared to a diseased nerve (Median nerve in patients with CTS).

Hypothesis: There will be greater change in cold and vibration detection thresholds and NCS parameters in the median nerve compared to the ulnar, due to the lower functional baseline of the median nerve.

Our third goal involves comparison among the 3 intervention groups, specifically we aim to compare the effects of manual acupuncture (MA) to those of low-frequency (LF_EA) and high-frequency electroacupuncture (HF-EA).

Hypothesis: High-frequency electroacupuncture will have greater effect on NCS, QST followed by low-frequency electroacupuncture and manual acupuncture, in accordance to traditional practices.

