Specific Aim 2: For the current study, the Ulnar nerve is serving as a healthy control to allow for comparison to the diseased Median nerve post-intervention. Historic studies measuring the local, direct effect of acupuncture on a healthy nerve or studies comparing the local effects of acupuncture on a healthy versus a diseased nerve are not available. With respect to our Specific Aim 2 hypothesis, the Ulnar nerve is serving as a disease-free control condition, wherein acupuncture-dependent change in QST and NCS in the Ulnar nerve is anticipated to be largely negligible as the nerve is already functioning at optimal physiologic parameters. Due to this expectation of negligible treatment effect in the Ulnar nerve, the proposed sample size from Specific Aim 1 (20 subjects per acupuncture modality) is expected to be sufficient for these comparisons within each type of acupuncture. Further, we plan to carry out the Median/Ulnar nerve comparisons separately for each of the 3 intervention modalities. The use of both Median and Ulnar nerves lets the treatment as well as control conditions of interest come from the same subjects, allowing them to serve as their own controls. However, this repetition design warrants the use of mixed-model analysis so the random-effects portion can account for the intra-subject serial correlation expected with repeated measurements.

Specific Aim 3: With regards to the proper sample size for comparison among the 3 types of acupuncture – we based the sample size calculation for each study arm in part on the effect sizes observed by Lang et al (42), who enrolled 24 healthy subjects in 6 groups involving a cross over between manual, low-frequency and high-frequency acupuncture and were able to observe significant differences in QST (CDT) between the 3 acupuncture modalities, $p=0.0034$. In our current study, the cross-over design is based on the comparisons of Median and Ulnar nerves; however, the individual methods of acupuncture will be populated by different cohorts. For this reason, the random-effects blocking of our mixed- models will have the nerve dependence

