9.4. Statistical Analysis Plan

Primary statistical analysis for all 3 Specific Aims will use linear mixed-effect models to evaluate the effects of treatment group and intervened nerve location on the outcome measures described above. A mixed-model design will be used to create an intention-to-treat framework

and allow for any missing data. Principal assessment will be on the change in outcomes resulting from acupuncture intervention, calculated as the difference in outcomes before and after treatment. These outcomes will include CDT and VDT, distal motor/sensory latencies, CMAP and SNAP amplitudes, CMAP area and duration, nerve conduction velocities (Specific Aim 1). Acupuncture characterization will be carried out first in the Median and Ulnar nerves of the arm (Specific Aims 1, 2). In both Median and Ulnar nerve interventions, group will be a three level factor based on the type of acupuncture - MA, LF-EA and HF-EA (Specific Aim 3).

Specific Aims 1 and 2:

As a principal independent variable, location of the intervention will be a four-level factor encompassing the possible combinations of treated and evaluated nerves. For Specific Aims 1 and 2, these levels will be: MM – Median treated and tested, MU – Median treated and Ulnar tested, UM – Ulnar treated and Median tested, and UU – Ulnar treated and tested. A time variable (Week 1, Week 2) will also be included to test for any effects due to order of the treated nerves. Additional covariates known to be associated with QST and NCS outcomes such as age and gender will be corrected for as well. Secondary analysis will include treatment evaluations of outcomes within each location of intervention and additional contrasts between the four time points (pre and post treatment for both Week 1 and Week 2). Persistence of the acupuncture effects will specifically be assessed by comparing changes in outcomes after the first treatment but before the second session.

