Another way to characterize the wash-out effect of acupuncture is to compare baseline data from Week 1 and Week 2. We will perform an exploratory analysis to assess for an interaction between location and time, in a mixed linear model. We will incorporate nerve location, evaluation time and the location-time interaction to check for dependencies between Week 1 and Week 2. As stated, the dependent outcomes of all models are the change in QST and NCS from baseline to post-acupuncture. This will allow for a full assessment of washout and carry-over effects with respect both to the nerve location (healthy Ulnar vs diseased Median), time (Week 1 vs Week 2) as well as the order of nerve assessment (the interaction). However, with the repeated nerve measures, it will still be necessary to utilize a mixed-model approach so that the random-effects blocking (nerve location dependent on subject) will allow for the intra-subject serial correlation. For the final model, although exploration of the wash-out effect will be critical, it will pose to be impractical to keep all these covariates in the final model. Only significant time-dependent interactions will be included since the model would otherwise suffer from overfitting due to too many covariates and the limited sample size.

Specific Aim 2: Following completion of Specific Aim 1, we expect to see significant acupuncture effect on the Median nerve (within each acupuncture group). In our proposed mixed linear model for Specific Aims 1 and 2 this would represent MM on the level of each individual group (MA, LF-EA, HF-EA). Conversely, we do not expect to observe a significant effect of acupuncture on the healthy Ulnar nerve as it is already functioning at optimal physiologic level. This would be the UU at the level of each individual group and corresponds to a clinical control. We will conduct direct contrasts between MM and UU as part of the mixed linear model with nerve location, time dependencies and random-effects grouping following the same design as in Specific Aim 1.

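### Aim 1's locality claim rests on comparing a diseased nerve with a healthy one; the same-nerve contrast (median tested after median versus after ulnar needling) is in the model but never named

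*Combined protocol and SAP*

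**What the plan says.** Section 1.1 states the QST hypothesis of Aim 1: cold and vibration thresholds fall "in the underlying nerve sensory distribution only". Sections 3 and 9.3 repeat it.

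Section 3, under local effects, gives the route: "In this way we will explore whether acupuncture has effects only on the underlying nerve, or also on a neighboring nerve". It adds that this is done by "measuring post-acupuncture QST and NCS in both the median and ulnar nerves, when the intervention is done over the median nerve". No formal test is stated there.

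Section 9.4 says the primary mixed models will "evaluate the effects of treatment group and intervened nerve location on the outcome measures described above". It defines the main factor: "location of the intervention will be a four-level factor encompassing the possible combinations of treated and evaluated nerves". The levels are MM, MU, UM and UU, with the treated nerve first and the tested nerve second. A week term is included. It continues: "Secondary analysis will include treatment evaluations of outcomes within each location of intervention". The only contrast between cells that 9.4 names is MM against UU, which belongs to Aim 2. UM otherwise appears only as an optional substitute in the modality model, which the plan puts beyond the scope of Aim 3.

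On the ulnar nerve, 9.1 says that acupuncture-dependent change "is anticipated to be largely negligible as the nerve is already functioning at optimal physiologic parameters". The Aim 2 text of 9.4 agrees: "we do not expect to observe a significant effect of acupuncture on the healthy Ulnar nerve".

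**The concern.** Every subject has a diseased median nerve and a healthy ulnar nerve. Going from MM to MU therefore changes two things at once: whether the needles lie over the tested nerve, and whether that nerve is diseased. If a healthy nerve cannot improve much, a null MU is expected even when acupuncture acts on the whole arm or the whole body, so it says little about spread.

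Testing the four-level factor as a whole would not help (the plan does not say whether it will), because the factor mixes treated and tested nerve and can be significant through disease status alone. Reading MM as significant and UM as not significant is not a test of their difference.

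At stake is the answer to Aim 1's own QST hypothesis. There is no sham or no-needle arm, so the median nerve tested after ulnar needling (UM) is the closest control in the data. MM against UU, and the pooled t-test in 9.3, are Aim 2 comparisons and are not at fault here.

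**Working it through.** **Inputs.** From 9.1: CDT change δ = 0.35 °C; variance of change 0.696, so SD = √0.696 = 0.834; α = 0.05, taken as two-sided because the protocol does not say; 20 per arm, 60 pooled. Assumed, because the documents give no value: correlation r = 0, 0.3 or 0.5 between the four change scores of a subject, with equal variances.

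**The plan's own figure.** 9.1 gives no power for a locality contrast. Its 20 per arm for a 0.35 °C CDT change does not reproduce as a pre-post test: n = (0.834 × (1.960 + 0.842) / 0.35)² = 44.6, so 45; power at 20 is 43% (t-test). That is a separate matter, and nothing below depends on it.

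**What each contrast estimates.** Let the median nerve improve by δ when needled directly and by λδ when the ulnar nerve is needled (λ = 0 wholly local, λ = 1 wholly non-local). Take the ulnar change as 0, as the plan expects.
- MM − MU = δ − 0 = 0.35, whatever λ is.
- MM − UM = (1 − λ)δ: 0.35 if local, 0 if non-local.

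**Power of the paired contrasts.** SD of a difference = √(0.696 × 2(1 − r)) = 1.180, 0.987, 0.834. At n = 60 the noncentrality 0.35√60/SD is 2.30, 2.75, 3.25, giving 62%, 77%, 89%. At n = 20 it is 1.33, 1.59, 1.88, giving 24%, 33%, 43%.

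**Four-level factor as a whole, n = 60.** F with 3 and 177 df; noncentrality = 60 × Σ(mean − grand mean)² / (0.696(1 − r)). At r = 0 this is 60 × 0.1225/0.696 = 10.56 (non-local) and 60 × 0.0919/0.696 = 7.92 (local).

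| Significant result (r = 0 to 0.5) | Wholly non-local | Wholly local |
|---|---|---|
| MM−MU, n = 60 | 62–89% | 62–89% |
| MM−UM, n = 60 | 5% | 62–89% |
| Whole factor, n = 60 | 78–98% | 64–93% |
| MM−MU, n = 20 | 24–43% | 24–43% |
| MM−UM, n = 20 | 5% | 24–43% |

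**If the ulnar nerve does respond (non-local case).** With half the median response, MM−MU = 0.175 °C and is significant in 20–36% (n = 60) or 10–15% (n = 20). With an equal response it is about 5%.

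**Informal reading, MM significant and UM not (simulation, 40,000 trials per setting).** Wholly non-local: 7–10% at n = 60, 17–24% at n = 20. If UM responds half as much as MM (0.175 °C): 54–57% at n = 60, 33–37% at n = 20, although the effect is then not confined to the underlying nerve.

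**Reading 0.696 as an SD.** It equals √((0.9² + 0.4²)/2), the pooled SD of the two CDT values in 9.1, so it may be mislabelled. At n = 60, MM−MU is then significant in 77–97% in both cases, and MM−UM in 77–97% if local and 5% if non-local. The contrast between the two columns is unchanged.

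**The case against.** The strongest reply is that Section 3 describes the role of the ulnar nerve and specifies no MM−MU test; the analysis is in 9.4, where UM is a factor level and is evaluated in its own right. Under a wholly non-local effect, UM alone would be significant in about 89% of trials at n = 60, so the error would usually show, and the informal misreading is limited to 7–10%. This stands for the pooled data and for a wholly non-local effect. It does not stand at n = 20, where UM alone is significant in only 43%, or for partial spread, where the informal reading goes wrong in more than half of pooled trials. That last figure illustrates the lack of a direct test rather than the disease confounding, and MM−UM itself would detect the difference in only 20–36% of such trials.

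The documents are also not uniform on a zero ulnar response. Aim 2 predicts only a greater change in the median nerve, and 5.2 reports that one session may alter the parameters of either nerve when its own points are needled. With a real ulnar response the confounding shrinks, as shown above. But 9.1 and 9.4 both state the negligible expectation, and the analysis should not depend on that being wrong.

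Finally, MM and UM come from different weeks, while MM and MU share a session. Carryover is therefore a real weakness of MM−UM; the counterbalanced order, second baseline and week term reduce it but do not remove it.

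**Conclusion.** The concern holds. The stated route to the locality question cannot separate a local from a general effect when the healthy nerve responds little, which is what the plan expects: an MM−MU test is significant in 62–89% of pooled trials in either case. The same-nerve contrast separates the two (5% against 62–89%) and loses no power relative to MM−MU under these assumptions. The figures rest on 0.35 °C, a variance of 0.696, no ulnar response, and an assumed correlation of 0 to 0.5.

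The gap lies in the pre-specified text. The data are collected and the cell is modelled, and the study is an exploratory pilot without multiplicity adjustment. It should be fixed, because it concerns how the primary hypothesis is answered and because a contrast chosen after the data are seen is weaker evidence.

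**What to change.** In 9.4:
- Name MM−UM as the main Aim 1 locality contrast, for CDT and VDT first, estimated from the existing four-level mixed model with the week term and pooled over the 60 subjects. Name UU−MU as supporting, with little signal expected.
- Report the UM and MU changes with 95% confidence intervals, and state that a non-significant UM is not read as absence of spread.
- Keep the within-modality MM change as planned, but do not conclude locality from it or from MM beside MU alone. Leave MM against UU to Aim 2.
- Report a Week 1-only MM against UM comparison as a descriptive carryover check.
- State that MM−UM does not remove effects of where the needles are retained during QST, or expectation in subjects who recognise the target nerve.

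The cost is one contrast statement and a few sentences, with no new data. The limits should be stated too:
- Pooled power for a local 0.35 °C effect is 62%, 77% or 89% (r = 0, 0.3, 0.5), against 89% for the pre-post MM test; within one modality it is 24–43%.
- At n = 60 the 95% half-width is 0.216–0.305 °C for MM−UM and 1.96-type precision of about 0.22 °C for UM, so a UM change of 0.175 °C could not be excluded.
- A carryover shift of 0.1, 0.2 or 0.35 °C in the Week 2 UM change of one order biases MM−UM by half that amount and raises false positives to 6–7%, 10–15% or 21–36%.
- The Week 1-only check (30 against 30) avoids carryover but has 36% power and a half-width of 0.43 °C.
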